#### 4.3.5 Gastrointestinal symptoms associated with GERD over time

##### 4.3.5.1 Methods of assessment

###### GERD symptoms

The method of assessment of symptoms will be a questionnaire in the CRF. At each visit, the presence of symptoms will be assessed retrospectively by the investigator in a standardized manner. The definition for each symptom is:

- heartburn a burning feeling, rising from the stomach or lower part of the chest up towards the neck
- acid regurgitation flow of sour or bitter fluid into the mouth
- dysphagia difficulties in swallowing

###### Other GI symptoms

- epigastric pain Pain centred in the upper abdomen
- flatulence The presence of excessive amounts of air or gases in the stomach or intestine, leading to distension of the organs
- bloating A tightness located in the upper abdomen; it should be distinguished from visible abdominal distension
- diarrhoea abnormal frequency and liquidity of faecal discharges.

and will be classified as:

none:

mild: awareness of symptoms, but easily tolerated

moderate: discomfort sufficient to cause interference with normal activities

severe: incapacitating, with inability to perform normal activities

-Ability to vomit The forcible expulsion of the contents of the stomach through the mouth

-Ability to belch Eructation, the noisy voiding of gas from the stomach through the mouth

#### **4.3.5.2 Calculation or derivation of endpoint**

Not applicable.

#### **4.3.6 Per-operative events**

##### **4.3.6.1 Methods of assessment**

The assessment of per-operative complications will be made in a standardized manner and recorded in the CRF:

- Bleeding
- Perforation
- Pneumothorax
- CO2 retention
- Emphysema
- Other complications

Total operation time, completion of surgical procedure, type of fundoplication and if crural repair was done or not will be recorded in the CRF.

##### **4.3.6.2 Calculation or derivation of endpoint**

Not applicable.

#### **4.3.7 Post-operative symptoms and events**

##### **4.3.7.1 Methods of assessment**

The method of assessment of short term (< 30 days) post-operative lapse and symptoms will be made by the investigator in a standardized manner and recorded in the CRF at visit 6 for operated subjects to ensure a smooth post-operative recovery.

- Post-operative hospital stay (days).
- Abdominal infection.
- Other abdominal complications.
- Pulmonary infection.
- Other pulmonary complications.
- Bleeding
- Other complications
- In hospital post-operative death
- Other post-operative symptoms

##### **4.3.7.2 Calculation or derivation of endpoint**

Not applicable.

#### **4.3.8 24 hour pH metry, manometry and SAP**

##### **4.3.8.1 Methods of assessment**

###### 24 hour pH metry

Intra-esophageal and intra-gastric acid exposure as assessed by 24 hr pH metry, where Intra-esophageal pH monitoring is mandatory. The 24 hr pH -monitoring will be initiated at visit 1 or visit 3 to document the subject's reflux pattern. Each investigational centre will use their standard equipment for ambulatory pH -recording, including standard analysis software. Manometry will be made in all subjects at the first pH metry occasion according to local standards. After at least four hours of fasting and topical anaesthesia of the nostril, the pH -electrode (preferably a 2 way channel will be positioned, 1 in the distal esophagus and 1 in the proximal stomach, with the esophageal recording tip 5 cm above the oral margin of the lower esophageal sphincter, the location which is determined by manometry). The electrode will be connected to a data recorder.

During the recording time the subject will be at home or at work and will be instructed to live as normal as possible including participating in normal daily activities and taking meals. Acidic food, beverages and intake of alcohol are not allowed. Furthermore, the subjects will be told not to take

any medication that interferes with the recording, such as acid reducing compounds and PPIs. However, at visit 7 and 16 the subjects randomized to medical treatment should continue their treatment during the pH metry.

After 24 hours the subject will return to the laboratory, the data will be downloaded to the host computer and the data from the recorder will be analysed by the software program. A visual check of the pH-curve will be carried out to discover electrode drift or interference in the recording.

The fraction of time during which  $\text{pH} \leq 4$  for the total, upright and supine periods will be calculated from the pH data. If the pH -monitoring is inadequate for technical reasons or is discontinued within 18 hours, the recording should be repeated. Results will be recorded in the CRF. The data will be sent to AstraZeneca.

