**Subjects untreated with PPI prior to study start will (if possible):**

- (i) start the run-in period with the “investigational week” at visit 1. In such cases an endoscopy with biopsy sampling will be made at visit 1. If insufficient biopsies have been taken at visit 1 then another endoscopy with biopsy sampling will be done at visit 3. In cases of mucosal breaks classified as LA grade C or D at visit 1 or 3 a new endoscopy must be performed at visit 4 prior to randomization. Furthermore, laboratory measurements, 24 hr pH metry, manometry and SAP will be made. If these assessments can be made within 2 weeks from visit 1 then visit 2 and 3 can be left out. The study drug (esomeprazole 40 mg o.d.) will then be dispensed and the subject will continue the run-in period. If the time between first endoscopy (visit 1) and the 24 hour pH metry is more than 2 weeks, the study drug must be dispensed at visit 1 and the subject will follow the same routine as the **treated subject (i)**.

10-year study period

If reflux esophagitis LA grade C or D is found at visit 3, a new endoscopy must be done at visit 4 prior to randomization.

- Subjects will be randomized to either medical treatment or surgery at visit 4. Medical treatment is 20 mg o.d. (start dose) and can be adjusted, but is not to exceed 40 mg daily. Surgery must be performed within 3 months after randomization. The subject is allowed to be treated with esomeprazole 20 mg o.d. and can be adjusted, but is not to exceed 40 mg daily whilst awaiting the surgery. Visit 5 and 6 will only be attended by subjects randomized to surgery.
- Endoscopy with biopsy sampling will be performed at visit 8, 12, 16, 33 and 39. A 24 hour pH metry and SAP will be performed at visit 7 and 16. Endoscopy will be performed at extra visits in case of symptomatic relapse or early discontinuation. A 24 hr pH metry and SAP should be performed in case of dose adjustments (prior to).
- Symptoms will be assessed at each visit except at visit 5 and the telephone visits (visit 30, 32, 34, 36, 38). Laboratory screen will be done at visit 8, 12, 16, 33 and 39 and at early discontinuation visits.
- Patient reported outcomes (PRO) will be assessed by QOLRAD and GSRS at visits 4, 8, 10, 12, 14, 16, 31, 33, 35, 37 and 39 and at early discontinuation visits.
- Body weight will be assessed at visits 4, 8, 12, 16, 33, 39 and at extra visits and at early discontinuation visits.

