- All serious adverse events and those adverse events causing premature discontinuation of study drug and/or study will be recorded at each visit except visit 1 and 5 (surgery visit).

During the 10-year study period subjects in both treatment arms having (moderate-severe) recurrent GERD symptoms on at least **3 consecutive days** will be instructed to contact the clinic. The subject will be asked to answer the questions regarding treatment failure and follow the instructions for each treatment arm. In case of dose adjustments, the increased dosage must be taken for 8 weeks before a second dose adjustment is made. A 24 hr pH metry and SAP should be made prior to dose adjustment (only applicable to an adjustment to a higher dose). If the subject is symptom-free and satisfied after this treatment period with an increased dose, a reduction to the previous lower dose should be aimed at. At least one attempt to return to the previous lower dose should be made. After two periods of dose increase due to recurrence of symptoms, the investigator can decide which dose is required to maintain symptoms under control for the remaining study period, but the dose cannot exceed 40 mg o.d. or 20 mg b.i.d.

[figure not shown]
In case of subjects who are satisfied with their treatment, but with temporarily (at least **3 consecutive days**) moderate-severe GERD symptoms, the subject will be offered an endoscopy and:

- Subjects in the medical arm will then receive treatment with esomeprazole 40 mg o.d. for 2-12 weeks according to endoscopic findings and symptomatology. After treatment the subject in the medical arm will continue the study with esomeprazole at a dose which is required to maintain symptoms under control but does not exceed 40 mg daily.
- Subjects in the surgical arm are allowed to have symptomatic treatment (antacids) and will continue the study.

Visits 5 and 6 are only relevant to subjects randomized to surgery.

Interim analyses are planned 3 years (visit 12) and 5 years (visit 16) after last subject randomized (medical arm) or operated (surgical arm) on, to evaluate efficacy and tolerability.

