**Table 2 Study plan prolongation**

Visit Nos.	16 a	30 b	31	32 b	33	34 b	35	36 b	37	38 b	39	Extra visit	Discont. Visit h
Year	5 ±6w	5.5 ±6w	6 ±6w	6.6 ±6w	7 ±6w	7.5 ±6w	8 ±6w	8.5 ±6w	9 ±6w	9.5 ±6w	10 ±6w		17
	X												
Endoscopy incl. biopsies Hp status	X				X						X	X f	X
24 hr pH metry, manometry & SAP c												X g	X
QOLRAD, GSRs	X		X		X		X		X		X		X
Symptoms	X		X		X		X		X		X	X	X
Laboratory screen	X				X						X		X
Body weight	X				X						X	X	X
Dispense study drug d	X		X		X		X		X			X	
Compliance d	X		X		X		X		X		X	X	X
Concomitant Medication	X		X		X		X		X		X	X	X
AE e	X	X	X	X	X	X	X	X	X	X	X	X	X
Informed consent and blood sample for genetic research (optional) i	X												

- a Last Visit in the 5-year LOTUS study
- b Telephone Visit (hospital visit optional)
- c If pH monitoring was less than 18 hours, pH metry should be repeated
- d Only for Subjects in the medical arm
- e All SAE and those AE causing premature discontinuation of study drug and/or study
- f In case of administration of healing dose (esomeprazole 40mg o.d)
- g In case of increased dose
- h In case of premature discontinuation
- i See appendix O

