### **3.3.5.4 Procedures for discontinuation**

The subject should return for a clinic visit at the time of, or soon after discontinuation with maintained medication (medical arm) for the following assessments:

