#### **Discontinuation after randomization:**

- Endoscopy including biopsies and *Hp* status
- Laboratory screening
- Body weight
- All SAE and those AE causing premature discontinuation of study drug and/or study
- Patient reported outcomes
- Symptoms
- 24 hour pH metry and SAP
- The reason for discontinuation

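### The protocol contradicts itself on whether medical-arm pH metry at discontinuation is on or off esomeprazole, leaves pre-adjustment recordings off drug by default, and gives two triggers for them

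*Protocol*

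**What the plan says.** **Drug status during the recording.** Section 4.3.8.1 of the protocol tells subjects not to take "any medication that interferes with the recording, such as acid reducing compounds and PPIs". It then makes one exception: "at visit 7 and 16 the subjects randomized to medical treatment should continue their treatment during the pH metry". Extra visits and the discontinuation visit are not named.

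**Discontinuation.** Section 3.3.5.4 has the subject return "at the time of, or soon after discontinuation with maintained medication (medical arm) for the following assessments". For discontinuation after randomization the list includes "24 hour pH metry and SAP".

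**Which dose changes need a recording.** Section 3.1 speaks twice on this, both times for the 10-year study period. The bulleted list says: "A 24 hr pH metry and SAP should be performed in case of dose adjustments (prior to"; there is no limit on direction. The later text on recurrent symptoms says: "A 24 hr pH metry and SAP should be made prior to dose adjustment (only applicable to an adjustment to a higher dose". Table 1 note 16 (years 0 to 5) refers to dose adjustment without qualification. Table 2 note g (years 5 to 10) says: "In case of increased dose".

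**Use of the data.** Table 3 lists pH and Symptom Association Probability as other, descriptive endpoints. Section 6.2.3 summarises intragastric pH and Symptom Association Probability by mean and SD, by visit and treatment group.

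**The concern.** A pH recording on a proton pump inhibitor and one off it measure different things: acid exposure under treatment, and acid exposure with treatment withheld. For the medical arm the protocol must therefore fix the condition at every recording. It does so at baseline and at visits 7 and 16. It does not do so for the two remaining occasions, which are the ones linked to loss of symptom control or to leaving the study.

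A site that follows Section 4.3.8.1 would record discontinuing medical-arm subjects off drug; a site that follows Section 3.3.5.4 would record them on drug. Both sets of values would enter the same discontinuation-visit mean for the medical arm. Before dose changes, the two triggers would also lead sites to record different subsets of steps. The resulting summaries could not be read as acid control on the current dose, nor set against visits 7 and 16.

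**Working it through.** No sample size, power or error-rate figure is involved, so the check sets the passages side by side.

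**Step 1: drug status in the medical arm, by occasion.**

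| Recording | Section 4.3.8.1 | Any other rule | Result |
|---|---|---|---|
| Baseline (visit 1 or 3) | Off | Sections 3.1 and 3.4.5: esomeprazole stopped at least 7 days before the visit 3 recording | Consistent, off |
| Visits 7 and 16 | On (the exception) | None | On |
| Extra visit, before a dose adjustment | Not in the exception, so off | None; Section 3.3.5.4 covers discontinuation only | Off if read literally; no washout stated |
| Discontinuation after randomization | Not in the exception, so off | Section 3.3.5.4: on | Contradiction |

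Of the four kinds of recording, two are clear. One is a direct contradiction. One is settled only by default, and incompletely: Section 3.4.5 gives the 7-day stop as the condition for relevant pH measurements at visit 3, but no stop is stated for extra visits. Leaving out tablets only for the recording matches neither the baseline condition nor the visit 7 and 16 condition.

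**Step 2: the trigger, by type of dose change.** The steps are those in Sections 3.1 and 4.1.

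| Dose change | Daily dose | Section 3.1 list, Table 1 note 16 | Section 3.1 later text, Table 2 note g |
|---|---|---|---|
| 20 mg o.d. to 40 mg o.d. | 20 to 40 mg | Recording | Recording |
| 40 mg o.d. to 20 mg b.i.d. | 40 to 2 × 20 = 40 mg | Recording | Unclear |
| Return to the previous lower dose | Lower | Recording | No recording |

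The passages agree only on the first row. In the second, Section 4.1 describes the dose as changed, where the earlier step is an increase, yet it presents this step as the second dose adjustment. It therefore falls under the wider trigger and may or may not fall under the narrower one. The third row is not rare by design, since Section 3.1 asks for at least one attempt to step back down.

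The split is not simply one rule for years 0 to 5 and another for the prolongation. Both Section 3.1 statements cover the 10-year period, so each table note conflicts with one of them.

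**Step 3: reach.** After visit 16, Table 2 places pH metry only at extra visits and the discontinuation visit. Every medical-arm recording in the five-year prolongation is therefore outside the Section 4.3.8.1 exception.

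**Step 4: effect on the analysis.** Section 4.1 decides treatment failure in the medical arm from two questions, on symptom control and on need for other regular drugs. No pH value enters. The effect stops at the descriptive summaries of Section 6.2.3.

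**The case against.** The case for leaving the text alone has four parts.

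- *The visit-specific rule governs.* Section 3.3.5.4 is written for the discontinuation visit and might be taken to override the general rule. That is a sensible reading, but Section 4.3.8.1 names its exceptions and omits this visit, so a site following the pH method section would do the opposite.
- *The later text in Section 3.1 clarifies the list.* This is plausible, and Table 2 note g agrees with it. Table 1 note 16 still carries the wider wording, and the once-daily to twice-daily change stays unsettled.
- *Summaries are by visit, so nothing is merged with visits 7 and 16.* True, and further table rules may stand in the statistical analysis plan, which is not at hand. Mixing within the discontinuation visit remains.
- *Medication use is already recorded.* Section 3.4.5 requires this in the CRF, but does not ask for the last tablet before a recording.

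The objection is also right that stronger readings fail. A reader might infer any of the following:

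- *Section 3.3.5.4 puts pre-adjustment recordings on drug.* It does not; it concerns discontinuation only.
- *The recordings would show untreated reflux.* This is not shown, because no washout is stated for extra visits.
- *The recordings cannot show whether a dose was failing.* This is too strong: if Section 3.3.5.4 is followed, the discontinuation recording is made on the failing dose.
- *They are the only objective evidence when symptoms return.* Endoscopy is also done at symptomatic relapse and at discontinuation.
- *The last step before failure needs no recording.* The text is unclear on this; it does not say so.

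**Conclusion.** The point holds as an internal contradiction with a limited effect. Three things are established:

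1. Sections 4.3.8.1 and 3.3.5.4 give opposite drug status for medical-arm pH metry at discontinuation.
2. Pre-adjustment recordings are off esomeprazole by default, with no washout stated, and so are not comparable with visits 7 and 16.
3. Section 3.1 and the two table notes give two triggers, and leave open whether the change from 40 mg o.d. to 20 mg b.i.d. is covered.

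The consequence falls on descriptive pH and Symptom Association Probability summaries in the medical arm, including all such recordings after visit 16. The primary endpoint is untouched.

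The number of affected recordings cannot be derived. A reader might take the 70% success assumption in Section 6.1, compute 0.30 × 275 = 82.5, about 83 failures, and multiply by one discontinuation and two step recordings to reach 3 × 83 = 249. The documents do not support this. Section 6.1 assumes success of at least 70%, so 83 is a ceiling under that assumption. The factor of three presumes a recording at the very step whose status is unclear; without it the product is 2 × 83 = 166. Subjects who change dose but do not fail, discontinuations for other reasons, repeated increases and years 5 to 10 are all left out. The figure is neither an estimate nor a bound.

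The conclusion assumes only that sites follow the text as written. It should be corrected, but it does not threaten the main comparison.

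**What to change.** - Reconcile Section 4.3.8.1 with Section 3.3.5.4, so that one medical-arm recording condition is stated for extra-visit and discontinuation recordings as well as for visits 7 and 16. If any recording is to be off drug, state for how long.
- Reconcile the two statements in Section 3.1, Table 1 note 16 and Table 2 note g to one trigger, and say explicitly whether the change from 40 mg o.d. to 20 mg b.i.d. is included.
- Record on/off status and the date of the last tablet with each pH recording.
- Tabulate on-drug and off-drug recordings separately in the pH and Symptom Association Probability summaries.

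Which condition and which trigger are right is for the sponsor and investigators to decide.

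The cost is wording in the affected sections and table notes, one small addition to the CRF and a split in the tables. No procedure is added beyond what one or other passage already requires.

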#### Symptom Association Probability (SAP)

Esophageal acid exposure and symptom reflux event correlation will be evaluated, this assessment is called Symptom Association Probability (SAP). SAP will be calculated according to [Shi G et al 1995](#), or [Weusten B et al 1994](#). Subjects with a positive SAP will be considered as having GERD.

#### **4.3.8.2 Calculation or derivation of endpoint**

Not applicable

### **4.4 Safety measurements and endpoints**

In this study will long-term treatment of esomeprazole be compared to anti-reflux surgery in the control of gastroesophageal reflux disease. The study is designed to study histological findings and changes in laboratory variables and not adjusted for non-serious reporting. The time between visits is too long to receive quality data for non-serious adverse events. The following safety variables will be recorded during the study:

- Histopathological changes in the squamous epithelium of the distal esophagus, the mucosa of the z-line and of the gastric mucosa as assessed by the use of the Sydney classification system (see Section [4.3.3](#) and appendix H)
- Changes in the laboratory screen variables (including serum gastrin, serum chromogranin A, Vitamin B12 and homocysteine)
- All serious adverse events and those adverse events causing premature discontinuation of study drug and/or study.

#### **4.4.1 Summary of safety objectives and endpoints**

[Table 4](#) shows how the safety endpoints of this study relate to the study objectives.

**Table 4 Safety objectives and endpoints relating to each objective**

Objective	Endpoints	Summary statistic for analysis (including timepoint and population)	Planned analysis	Significance of results
4.4.3 Laboratory screen variables	Laboratory assessments	
 
- Descriptive presentation of laboratory results for each sample occasion.
 
- Number of subjects with values below, within and above the reference range, over time.
 
- Median changes between baseline and the last visit for each laboratory variable.
 
- Graphs showing last visit values versus the baseline values for each laboratory variable.
 
-All clinical laboratory presentations will be made for the safety population.
 
	No formal statistical comparison.	The result will contribute to the determination of the adverse drug reaction pattern and frequency during long-term treatment with esomeprazole.
4.4.2 SAE and AE	Occurrence and nature (seriousness intensity and action taken to study drug due to AE) of all SAEs and AEs causing premature discontinuation of study drug and /or study.	
 
-Frequency of subjects with SAEs and AEs leading to discontinuation of study drug and/or study.
 
-AE pattern (e.g. by system organ classification)
 
- SAEs and discontinuations due to AE will be presented for the safety population
 
	No formal statistical comparison.	The result will contribute to the determination of the adverse drug reaction pattern and frequency during long-term treatment with esomeprazole.

The methods for collecting safety data are described below

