### 3. STUDY PLAN AND PROCEDURES

#### 3.1 Overall study design and flow chart

This study is designed as a 5-year, randomized, open, parallel-group multicentre trial with a 5-year prolongation with the objectives to estimate the efficacy and tolerability of esomeprazole compared with anti-reflux surgery, in a long-term treatment of adult subjects with confirmed, symptomatic gastroesophageal reflux disease with or without esophagitis (objectively documented by endoscopy and abnormal 24 hour pH metry). All subjects should be eligible for surgery.

The study will begin with a 12-week run-in period enabling the recording of baseline values and responses to medical treatment with esomeprazole 40 mg o.d. This period will end with a randomization into the 10-year study period. All subjects should have the need for continuous treatment to control reflux and be eligible for anti-reflux surgery. Subjects should not have more than LA grade B endoscopic-visualized mucosal breaks or more than mild symptoms of GERD prior randomization and should have responded to esomeprazole treatment in the 12-week run-in period.

The 10-year study period consists of 2 treatment arms, medical treatment (esomeprazole, start dose is 20 mg o.d.) and anti-reflux surgery (laparoscopic fundoplication). Subjects willing to accept randomization to either surgery or long-term medical treatment will receive treatment according to a randomization list.

*Helicobacter pylori* (*Hp*) status will be assessed based on biopsy material.

In case of confirmed peptic ulcer disease and positive *Hp* testing eradication therapy should be given prior to enrolment. Subject should not be enrolled within 3 months after therapy.

In case of a first episode of peptic ulcer disease during the 10-year study period and confirmed positive *Hp* testing eradication therapy is allowed.

In all other cases of *Hp* infection not associated with peptic ulcer disease eradication therapy is not allowed.

The planned number of subjects is 550 randomized in 11 countries, with at least 6 subjects per centre.

Visits 1, 2, 3, 4, 5, 6, 7, 8, 12, 16, 31, 33, 35, 37 and 39 will be regular visits with the investigator and visits 9, 10, 11, 13, 14 and 15 may be done by the study nurse.

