### **3.3.5 Discontinuation of subjects from treatment or assessment**

#### **3.3.5.1 Criteria for discontinuation**

Subjects may be discontinued from study treatment and assessments at any time, at the discretion of the investigator(s). A subject may, however, continue the study under exceptional circumstances (e.g. if continuation of study treatment or follow-up actions are necessary for the subjects safety and well-being, and the continuation of the study is not expected to be associated with any risk or discomfort for the subject). Specific reasons for discontinuing a subject from this study are:

1. Withdrawal of informed consent
2. Unwillingness to continue the study or lost to follow-up.
3. Any unacceptable adverse event, including laboratory result or physical findings, as judged by the investigator
4. Any “alarm symptoms” which, in the investigator’s judgement, requires treatment outside this protocol.
5. Continuous need for/intake of drugs listed under Section [3.3.4](#) criteria 7.
6. Protocol non-compliance as judged by the investigator
7. Classified as treatment failure
8. Pregnancy
9. Incorrect enrolment or randomization of subject
10. Other reason specified by the investigator.

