**Need for treatment other than esomeprazole for control of symptoms of reflux disease:**

In order to allow for a stringent assessment of treatment failure ask the following the question:

*“Do you have sufficient control of your heartburn and acid regurgitation?”*

If the answer is **No**, continue with:

*“Do you need other regular drug treatment to control your symptoms?”*

If the answer to this question is **Yes** and the dose of esomeprazole is 20 mg once daily, then the dose is to be increased to 40 mg once daily. The subject will be treated with the increased dosage for 8 weeks before a second dose adjustment can be made.

If the answer to this question is **Yes** and the dose is esomeprazole 40 mg once daily, then the dose is to be changed to 20 mg twice daily. The subject will be treated with the changed dosage for 8 weeks before being classified as a treatment failure if sufficient symptom control has not been achieved.

If the answer to this question is **Yes** and the dose is 20 mg twice daily, then the subject is a **treatment failure and will be withdrawn.**

b/ In the surgical arm:

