## **6. STATISTICAL METHODS AND DETERMINATION OF SAMPLE SIZE**

### **6.1 Determination of sample size**

The true rate of treatment successes (i.e. subjects who have not experienced treatment insufficiency within 5 years) is assumed to be at least 70% for both treatments. With 275 subjects on each treatment the true difference between treatment is, with a probability of 95%, not going to differ by more than 8 percentage points from the observed difference.

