### Safety analyses

The laboratory data will be presented in terms of median, Mean and SD for the baseline value, the last visit value and the change from baseline to last visit. A cross-table showing the number of subjects with the values below, within and above the normal range at baseline versus the same classification at the last visit will be provided for each laboratory variable. Graphs showing last visit values versus the baseline values and descriptive presentation over time will be presented for each treatment group and each laboratory variable.

Serious adverse events and AEs causing premature discontinuation of study drug and/or study will be presented descriptively.

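### SAEs and discontinuation AEs are summarised only as crude shares of subjects, although observation for them can end at different times in the two arms, so unequal observed time alone can separate the shares

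*Protocol*

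**What the plan says.** Table 4 of the protocol gives the summary statistic for these events as "Frequency of subjects with SAEs and AEs leading to discontinuation of study drug and/or study", presented for the safety population, with the planned analysis "No formal statistical comparison". The safety paragraph of Section 6.2.3 adds that "Serious adverse events and AEs causing premature discontinuation of study drug and/or study will be presented descriptively". Neither place gives a subject-time denominator, a timepoint or a time-to-event summary for these events.

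Other sections determine how long a subject is watched for SAEs:

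- Section 4.1: in either arm a subject who meets the failure question is a "treatment failure and will be withdrawn". Section 3.3.5.1 lists "Classified as treatment failure" among the reasons for discontinuation, and discontinuation there covers assessments as well as treatment.
- Section 4.4.2.2: SAEs are recorded at visits. After the last visit only events still ongoing are followed.
- Section 3.1: discontinued subjects who keep their consent are telephoned at 5 and 10 years. The listed topics are GERD surgery, GERD medication and symptoms; no SAE question is named.
- Synopsis, study centres and number of subjects: years 5 to 10 depend on a fresh request to take part.

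Section 3.1 states the aim "to estimate the efficacy and tolerability of esomeprazole compared with anti-reflux surgery". For relapses, Table 3 and Section 6.2.3 already use a subject-year denominator.

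**The concern.** A share of subjects with at least one event depends on both the event rate and the time over which events could be seen. Here that time is cut short by the primary endpoint itself, by other exits, and by the decision at year 5. The failure definitions in Section 4.1 differ by arm, so equal exit times cannot be taken for granted.

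Tolerability against surgery is a stated aim, and readers will set the two columns side by side whether or not a test is done. If one arm was watched for longer, its column will be higher for that reason alone. The crude shares give the reader no way to see whether this has happened, or in which direction.

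**Working it through.** **The protocol's own figure.** No figure is given for the safety comparison. The nearest is the 8-point precision in Section 6.1 (275 per arm, 70% success). The half-width is 1.96 × √(2 × 0.70 × 0.30 / 275) = 7.66 points, or 8.02 points after adding 1/275 as a continuity correction. The figure reproduces. It is the precision of an estimate, not an expected difference between arms.

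**Inputs from the protocol.** The duration is T = 10 years, and 5-year success "is assumed to be at least 70% for both treatments" (Section 6.1).

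**Assumptions, because the protocol gives no values.** Hazards are constant. The first-SAE rate s is the same in both arms, at 2, 5 or 8 per 100 subject-years. The other arm has 78% success at 5 years, for illustration. There are no other losses at first.

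**Formulas.**

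- Exit hazard: h = −ln(5-year success) / 5
- Mean observed years: (1 − exp(−hT)) / h
- Crude share with at least one SAE: s / (s + h) × (1 − exp(−(s + h)T))

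**Observed time.**

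- 70% success: h = 0.3567 / 5 = 0.0713, so (1 − 0.490) / 0.0713 = 7.15 years
- 78% success: h = 0.2485 / 5 = 0.0497, so (1 − 0.608) / 0.0497 = 7.88 years, a ratio of 1.10

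**Crude shares over 10 years, same true SAE rate in both arms** (gaps from unrounded values):

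| Assumed first-SAE rate per 100 subject-years | 70% success | 78% success | Gap, points |
|---|---|---|---|
| 2 | 13.1% | 14.4% | 1.3 |
| 5 | 29.0% | 31.6% | 2.7 |
| 8 | 41.2% | 44.8% | 3.6 |

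**A rate removes the gap.** At s = 0.05, mean time at risk for a first SAE is (1 − exp(−(s + h)T)) / (s + h) = 0.7028 / 0.1213 = 5.79 years in the 70% arm and 0.6310 / 0.0997 = 6.33 years in the 78% arm. Dividing the shares by these times gives 0.290 / 5.79 and 0.316 / 6.33, which is 5.0 per 100 subject-years in both.

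**Equal observed time.** With 70% success in both arms, both are observed for 7.15 years and the gap is zero at every SAE rate.

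**Reversed sign.** Add 3% per year of other discontinuation to the 78% arm only, so h = 0.0497 + 0.03 = 0.0797. Observed time falls to 6.89 years, below the 7.15 of the other arm. The shares become 13.1% v 12.7%, 29.0% v 28.0% and 41.2% v 40.0%.

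**Scale.** At T = 5 years, 70% v 78% gives 4.21 v 4.43 observed years and, at 5 per 100, shares of 18.7% v 19.7%. A wider contrast of 70% v 85% over 10 years gives 7.15 v 8.54 years and 29.0% v 34.0%. For comparison, the standard error of the 10-year difference at 29.0% v 31.6% with 275 per arm is √((0.290 × 0.710 + 0.316 × 0.684) / 275) = 3.9 points.

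**The case against.** The strongest reply is that counting subjects with SAEs is a conventional display, that nothing in Table 4 forbids adding rates, and that a statistical analysis plan, which Section 6.2.1 promises, may do so. That could remove the problem in practice. But Table 4 has a column for the summary statistic and fills it with the crude frequency, while the same protocol uses subject-years for relapses. The choice made is the weaker one for a 10-year trial with early exits.

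It is also fair that no test is planned, so any comparison is descriptive. That limits the consequence without making the shares comparable. Appendix P, which Section 3.1 cites for the follow-up calls, is not in the text available. If it asks about SAEs, the gap in observation is smaller.

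Three stronger readings are tempting, and the protocol does not support them:

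- A reader might infer that the arm with fewer failures will look less safe. The direction follows total observed time. It vanishes under the protocol's equal 70% assumption and can reverse, as shown above.
- A reader might take the 8 points in Section 6.1 as the expected difference in success. It is a precision, and 70% is a floor.
- A reader might say both shares are simply too low, because 5 per 100 subject-years implies 1 − exp(−0.5) = 39.3% at 10 years against a crude 29.0%. The 39.3% includes events after withdrawal. The purpose stated in Table 4 concerns adverse reactions during esomeprazole treatment, so it is not clearly the quantity wanted.

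**Conclusion.** The point holds as a conditional one. The protocol sets a crude share of subjects as its only summary of SAEs and discontinuation AEs, while observation for these events stops at failure, other discontinuation or non-entry to the prolongation. Whenever total observed time differs between arms, the shares differ at equal event rates, and the arm observed longer looks worse.

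In the 70% v 78% illustration the artefact is 1.3 to 3.6 points over 10 years, and at 5 per 100 it is smaller than the standard error of the difference. It grows with the imbalance and is smaller at 5 years. These sizes rest on constant hazards and assumed SAE rates. The 78% is an illustration, and the actual direction cannot be known from the protocol. The change is worth making because it is cheap and bears on a stated aim of the trial.

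**What to change.** In Table 4 and the safety part of Section 6.2.3, keep the crude count and add, by arm:

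- subject-years of SAE observation, up to the last visit or telephone visit at which SAEs were asked about;
- first SAEs per 100 subject-years of that observation, with time at risk ending at the first SAE;
- cumulative incidence of first SAE at 5 and 10 years, with subjects censored when SAE observation ends;
- for discontinuation AEs, cumulative incidence with treatment failure and other exits as competing events, because such an AE is itself an exit. This figure still depends on the failure rate, so show the competing exits beside it;
- a separate display of SAEs in the first 30 days after surgery. This is not planned at present: for the first post-operative month Section 6.2.3 covers post-operative complications, not SAEs.

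State that the descriptive between-arm tolerability statement rests on these figures. The cost is a few extra tables from dates already collected, with no new visits. The downside is that a single rate averages early operative and later risk, which is why the 30-day display and the cumulative incidence should accompany it. Censoring at exit also assumes that leaving is unrelated to later SAE risk, and the text should say so.
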